## 9 INVESTIGATIONAL PLAN

### 9.1 Overall study design and schedule of events

This will be a double-blinded, randomized, placebo-controlled, parallel-group study with the primary objective to evaluate the effect of oral supplementation with *Lactobacillus reuteri* on the frequency of confirmed UTI in adult women with recurrent UTIs.

The study will consist of a combined screening and randomization assessment, an IP first dose confirmation call, and monthly follow up assessments for six months. The screening and randomization assessment will be performed as a phone call or a video-call using an e-health digital platform. Informed consent will be signed via Bank ID. The monthly follow-up assessments will be performed either as a video-call or by phone. However, physical visits to the clinic at CTC AB might be performed for subjects in Uppsala.

Female subjects 18-50 years of age with recurrent UTI and currently on antibiotic treatment for UTI will be recruited from advertising (e.g. in social media, at pharmacies, etc.).

Recurrent UTI is defined as occurrence of at least two UTIs during the last six months or at least three UTIs during the last 12 months, with a minimum period of two weeks between episodes, unless there is a urinary culture confirming two different pathogens. The subject will contact the study site by phone or e-mail. Brief oral information about the study will be given and pre-defined pre-screening questions will be asked. Written information will be sent to the subject qualified for screening together with instructions regarding the e-health platform and Bank ID signing procedures.

During the screening and randomization assessment, full information about the study will be given and informed consent obtained as described in Section 13.3. Information regarding demographics, weight, height, medical history, UTI history, medication history, use of restricted products, and pregnancy will be collected and diet restrictions will be explained (see Section 10.6). Subjects will be screened for eligibility as per the pre-defined eligibility criteria (see Sections 10.4 and 10.5).

Eligible and consenting subjects will be randomized to intervention with either *Lactobacillus reuteri* or placebo. The subjects will be provided with IP for three months (90 days) and niture/Leu urine test kits. Instructions to start intake of IP as soon as the IP has been picked-up will be given.

The subjects will be contacted by study staff 1-3 days after randomization to confirm that first IP dose has been taken.

At the monthly assessments (video-call/phone-call or visit), the subject will be asked to answer pre-defined questions regarding symptoms (frequency, urgency and dysuria). If two out of three symptoms are present a UTI is confirmed. If only one symptom is present the subject will perform a niture/Leu urine test at home, preferably on urine retained in the bladder for approximately 3 hrs. If the test is positive (one of two analyses), a UTI is confirmed and the subject is recommended to contact the health care system for consultation regarding antibiotic treatment. Information on AEs, concomitant medications, use of restricted products, pregnancy, and compliance with instructions for IP intake will be collected.

An electronic diary will be used by the subject during the study period for recording of occurrence of UTI symptoms and sexual activity (frequency of intercourse, new partner, use of condom with spermicide).

The monthly follow-up assessment after six months will be the final study assessment. Number of empty sachets and any unused IP will be reported to CTC AB by the subject and documented by site staff on the IP accountability list.

The overall study design is shown in Figure 9.1. Assessments will be performed as described in Table 9.1. Each assessment is further described in Section 12.

[figure not shown]

Figure 9.1 Study Flow-chart

*Table 9.1 Schedule of events*

	Screen/ Random.	Intervention period				Follow-up		
		1 st dose	2	3	4	5	6	7
Assessment number	1	1	30±7	60±7	90±7	120±7	150±7	180±7
Day	-10 to 0	1	30±7	60±7	90±7	120±7	150±7	180±7
Informed consent	X							
Demographics	X							
Weight and height information	X							
Medical/surgical history	X							
UTI history	X							
Medication/product history	X							
Inclusion/exclusion criteria	X							
Randomization	X							
IP distribution triggered	X							
Confirmation of IP first dose call	X 							
IP intake		X						
Signs of recurrent UTI		X	X	X	X	X	X	X
AE reporting		X	X	X	X	X	X	X
Pregnancy information	X	X	X	X	X	X	X	X
Diary recordings (ViedocMe TM ) 		X						
Concomitant medications/products 			X	X	X	X	X	X

 1-3 days after randomization

 Information on sexual activity and signs of recurrent UTI.

 See Section 10.6 for restricted products.

## 9.2 Rationale for study design and dose groups

The study will be performed in female subjects aged 18-50 since this is the population expected to benefit from the intervention studied.

The study structure based on assessments using video -and phone-calls to ensure access to a broad population in a wide area although only one study site will be involved.

No clinical safety assessments are considered necessary considering the general good safety profile of probiotics.

## 10 STUDY POPULATION

### 10.1 Recruitment

Study subjects will be recruited using advertisement (*e.g* in social media, at pharmacies etc.) directed to pre-defined regions surrounding a number of IP distribution points.

### 10.2 Screening and enrolment log

The Investigator will keep records of all subjects screened and included. The reason for screening failure should be stated for all subjects screened but not included. The reason for withdrawal should be stated for all subjects included but not completed.

### 10.3 Number of subjects

A total of 140 subjects completed will be required, 70 in each intervention arm.

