#### 4 LIST OF ABBREVIATIONS AND DEFINITION OF TERMS

Abbreviation or term	Explanation
AE	Adverse Event
BMI	Body Mass Index
cfu	Colony-forming units
CTA	Clinical Trial Agreement
CV	Curriculum Vitae
DMP	Data Management Plan
DSM	Deutsche Sammlung von Mikroorganismen
DVP	Data Validation Plan
IEC	Independent Ethics Committee
eCRF	Electronic Case Report Form
EEA	European Economic Area
FAS	Full Analysis Set
GI	Gastro-intestinal
ICF	Informed Consent Form
IP	Investigational Product
N	Number
PAC	Proanthocyanidin
PPS	Per Protocol Set
RCT	Randomized Clinical Trials
SAE	Serious Adverse Event
SAP	Statistical Analysis Plan
SAR	Serious Adverse Reaction
SD	Standard Deviation
SDV	Source Data Verification
SOP	Standard Operating Procedures
SUSAR	Suspected Unexpected Serious Adverse Reaction
TMF	Trial Master File
UTI	Urinary Tract Infection
Enrolled subject	Subject who has signed the Informed Consent Form (ICF)
Screening failure	Enrolled subject not included

Included subject	Subject randomized
Withdrawn subject	Subject randomized but not completed
Completed subject	Subject completed both the intervention and the follow-up periods

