### **10.7.2 Subject replacement**

Withdrawn subjects will not be replaced.

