### 16.1 General

Data on continuous variables will be presented using summary statistics. Data will be presented in terms of number (N), arithmetic mean, standard deviation (SD), minimum and maximum value.

Categorical data will be presented as counts and percentages. Individual subject data will be listed by randomization number, and where applicable by assessment time.

All statistical tests will be performed using a two-sided hypothesis with a significance level of 5%.

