## **16.2 Determination of sample size**

Hypothesis:

$H_0$ : Mean number of UTIs in Probiotic group = Mean number of UTIs in the placebo group

$H_1$ : Mean number of UTIs in Probiotic group  $\neq$  Mean number of UTIs in the placebo group

The number of subjects needed to verify that the mean number of UTIs during six months for the probiotic will be 0.75 and for placebo 1.35 with a common standard deviation of 1.15, will be 118 (1:1 randomization) using a significance level of 5% and a power of 80%.

Assuming a drop-out rate of 15% a total of 140 subjects will be included.

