3.4 Number of Subjects

The number of subjects needed to verify that the mean number of UTIs during six months for the probiotic will be 0.75 and for placebo 1.35 with a common standard deviation of 1.15, will be 118 (1:1 randomization) using a significance level of 5% and a power of 80%.

Assuming a drop-out rate of 15% a total of 140 subjects will be included, 70 in each intervention arm.

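### The plan requires 140 completed subjects in three places, but its sample-size calculation makes 140 the number randomised, with about 119 expected to complete

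*Protocol*

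**What the plan says.** The target appears in two forms.

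- **As completers.** Protocol Section 10.3: "A total of 140 subjects completed will be required, 70 in each intervention arm". The protocol synopsis, under the planned number of subjects, and SAP Section 4.1, headed Sample Size Determination, carry the identical sentence.
- **As subjects included.** Protocol Section 16.2 derives 118 subjects, then adds: "Assuming a drop-out rate of 15% a total of 140 subjects will be included". The synopsis repeats this under statistical methods. SAP Section 3.4 gives the same derivation and ends: "Assuming a drop-out rate of 15% a total of 140 subjects will be included, 70 in each intervention arm".

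Protocol Section 4 fixes the vocabulary, and SAP Appendix 1 repeats it. An included subject is one who has been randomised, and a withdrawn subject is one who was randomised but did not complete. A completed subject is defined as: "Subject completed both the intervention and the follow-up periods". Protocol Section 10.7.2 adds: "Withdrawn subjects will not be replaced".

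**The concern.** Under these definitions, 140 included and 140 completed are the same number only if nobody drops out, yet the plan assumes that 15% will. Replacement is ruled out, so losses cannot be made up. The protocol and the SAP therefore each contradict themselves, and so does the synopsis.

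What is at stake is the recruitment target and how the trial is later described. A reader of Section 16.2 would take recruitment as finished at 140 randomised. A reader of Section 10.3 would say that the required number had not been reached and, on the plan's own drop-out rate, could not be. The completer figure also makes the design look stronger than the one that was calculated. Because SAP Section 4.1 gives only the completer figure under the sample-size heading, the error could pass unchanged into the study report.

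**Working it through.** **Inputs, all from the documents**

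- Protocol 16.2: "the mean number of UTIs during six months for the probiotic will be 0.75", against 1.35 for placebo, so the difference is 1.35 − 0.75 = 0.60. The common SD is 1.15 and allocation is 1:1.
- Protocol 16.2: "using a significance level of 5% and a power of 80"%. Section 16.1 makes the tests two-sided.
- Drop-out 15%; no replacement (Section 10.7.2).

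**Step 1. Reproduce the 118.** The standardised difference is 0.60/1.15 = 0.522.

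- Normal approximation: n per arm = 2 × (1.960 + 0.842)² × (1.15/0.60)² = 57.7, so 58 per arm and 116 in total.
- Two-sample t-test: 58.64, so 59 per arm and **118 in total**. This matches the plan exactly.

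**Step 2. Reproduce the 140.** 118/(1 − 0.15) = 138.8, so 139, or **140** with equal arms of 70. Hence 140 is the number to randomise, and 118 is the number before the drop-out allowance.

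**Step 3. Compare what each reading of 140 implies.** Power is for the two-sided t-test.

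| | 140 randomised | 140 completed |
|---|---|---|
| Randomised | 140 | 140/0.85 = 164.7, so 165 (166 with equal arms) |
| Expected completers | 140 × 0.85 = 119 | 140 |
| Completers per arm | 59.5 on average | 70 |
| Power | 80.6% (80.2% at exactly 59 per arm) | 86.5% |

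**Step 4. Size of the gap.** 140 − 119 = 21 completers. In women randomised it is 165 − 140 = 25, or 166 − 140 = 26 with equal arms.

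**Step 5. Look for another source of the completer figure.** Neither document contains a calculation that leads to 140 completers. The only derivation ends at 140 included. The list of changes in SAP Section 8 does not mention the number of subjects, so the SAP did not deliberately alter the target.

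**The case against.** The strongest reply is that this is one misplaced word. Both 118 and 140 reproduce, the sample-size sections make the intention clear, and the planned power is met whichever way 140 is read. That is correct, and it limits the finding: nothing here shows an underpowered trial or a miscalculated number. It does not remove the conflict, because the documents define both words and then use the wrong one in the very section that states the number of subjects.

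A second reply is that the documents never call the 118 completers. The Full Analysis Set, used for the primary objective, takes every randomised woman who had at least one dose (protocol 16.3.1; SAP 4.2.1 and 4.2.3), and data collected up to discontinuation are used (protocol 10.7.1). Some women who drop out may therefore contribute to the primary analysis, and power computed at 119 completers does not describe that set exactly. This stands as a caution about wording. Still, the plan itself obtains 140 by inflating 118 for drop-out, so 118 is by its own logic the number left after losses.

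A third reply is that no passage makes a completer count a criterion for stopping recruitment or for success. That is so; the consequence is an ambiguous target, not a breached rule. Finally, the SAP was first approved in August 2019 and the study was planned to finish in Q4 2018. If that timetable held, correcting the SAP could no longer affect recruitment, only the way the planned size is reported.

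**Conclusion.** The concern holds. The synopsis, protocol Section 10.3 and SAP Section 4.1 state a requirement of 140 completers that the plan's own calculation does not support and its own design would not deliver. The shortfall against the stated figure is about 21 completers, equivalent to 25 or 26 more women randomised.

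This rests on the plan's 15% drop-out rate, on its ban on replacement, and on its definitions of included and completed. The power figures rest also on its assumed means and SD and on a t-test of two means. On those assumptions, randomising 140 meets the intended 80%. It is an internal contradiction about sample size that should be corrected; it is not a power deficit.

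**What to change.** In the protocol synopsis (planned number of subjects), protocol Section 10.3 and SAP Section 4.1, replace the sentence with wording such as: *140 subjects will be randomised, 70 per arm; with 15% drop-out about 119 are expected to complete, against the 118 needed for 80% power before the drop-out allowance (protocol Section 16.2).* List the correction in SAP Section 8.

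The cost is one sentence in three places. There are no extra subjects and no change to the analysis. The stated completer figure falls from 140 to about 119, which is what the design supports.

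If the sponsor did intend 140 completers, Section 16.2 and SAP Section 3.4 must change instead, to 166 randomised in equal arms (140/0.85 = 164.7) with the matching power of 86.5%. That would cost 26 more women.

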### 10.4 Inclusion criteria

For inclusion in the study, subjects must fulfil the following criteria:

1. Willing and able to give informed consent for participation in the study.
2. Woman aged 18-50 years old, both inclusive, at screening.
3. Body Mass Index (BMI)  $\geq 18$  at screening.
4. Recurrent UTI, otherwise healthy. Recurrent UTI is defined as occurrence of at least two UTIs during the last six months or at least three UTIs during the last 12 months with a minimum period of two weeks between episodes, unless there is urinary culture confirming two different pathogens.
5. Currently on antibiotic treatment for UTI, at the time of screening .
6. Able and willing to comply with the restrictions defined for the study period (see Section 10.6).

---

 The intake of IP must be started during or within five days from stop of current antibiotic treatment for UTI.

7. Access to Bank ID and ability to use the e-health platform (i.e. Internet access).
8. Ability to understand and comply with the requirements of the study, as judged by the Investigator.

## 10.5 Exclusion criteria

Subjects must not enter the study if any of the following exclusion criteria are fulfilled:

1. Postmenopausal (defined as 12 months of amenorrhoea).
2. Pregnant or breastfeeding.
3. Planning to become pregnant during the study.
4. Irregular menstruations combined with perimenopausal symptoms.
5. Known hypersensitivity or allergy to any of the components of the test product, or to the comparator (placebo).
6. Currently on long-term antibiotic treatment.
7. Use of spermicide contraceptives including spermicidal condom within three days prior to first IP dose.
8. History of complicated cystitis, urgency incontinence, recent pyelonephritis, urological and/or gynaecologist abnormalities, as judged by the Investigator.
9. Unstable bowel disorder such as chronic or recurring diarrhoea, Crohn's disease, ulcerative colitis.
10. History of any clinically significant disease or disorder which, in the opinion of the Investigator, may either put the subject at risk because of participation in the study, or influence the results or the subject's ability to participate in the study.
11. Participation in any other clinical interventional study within 30 days before treatment.

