### 7.4 Risk/benefit assessment

#### 7.4.1 Summary of risk management

*Lactobacillus reuteri* probiotics are safe products that have been used for treatment and prevention of many types of disorders (28, 50, 51). The most common AE with a probable link to probiotics is the experience of flatulence that is usually restricted to the first days of intervention.

No clinical assessments will be performed in this study, thus there will be no risks associated with study procedures or devices.

Any possible AEs will be assessed in the current study.

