### **12.3.4 Medical/surgical history**

Medical/surgical history will be obtained during the screening interview to confirm eligibility.

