### **12.3.5 Urinary tract infection history**

Information regarding previous UTIs (diagnosis, prescriptions, etc.) during the last 12 months will be collected to confirm eligibility.

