## **12.4 Efficacy assessments**

### **12.4.1 Signs of recurrent UTI**

At the monthly assessments, the subjects will be asked to answer pre-defined questions regarding UTI symptoms: frequency (frequent voiding of urine), urgency (the urge to void immediately), and dysuria (pain in voiding and the absence of both fever combined with flank pain and unusual vaginal discharge). If two out of three symptoms are present a UTI is confirmed. If only one symptom is present the subject will perform a nitrite/Leu urine test at home, preferably on urine retained in the bladder for approximately 3 hrs. If the test is positive (one of two analyses), a UTI is confirmed and the subject is recommended to contact the health care system for consultation regarding antibiotic treatment.

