4.12 Deriving of confirmed and unique UTI

Definitions of confirmed UTI – If a subject have at least one of three statements:

- A total number of symptoms ≥ 2
- A positive urine test registered at site
- A positive test, self-reported

Definitions of unique UTI – If a subject have no confirmed UTIs within 14 days prior to the current confirmed UTI and have at least one of two statements:

- Confirmed UTI registered at site
- Confirmed UTI, self-reported and no confirmed self-reported UTIs within 14 days prior to the UTI (only applied to self-reported UTIs, since UTIs registered at site are assigned the date of telephone contact and not the date of the actual UTI)

Assigning dates to confirmed UTIs reported by site personnel: Date of previous telephone contact used if date is ≤ 14 days prior to registering in the UTI log. In case of later reporting of UTIs, the closest unmatched event date with indication of UTI prior to registration is used as date.

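### Standing frequency and urgency can be counted repeatedly as new UTIs, because the two-symptom rule does not ask for new symptoms and no entry criterion names this condition

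*Protocol*

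**What the plan says.** **Endpoint.** Protocol 12.4.1 sets the rule: "If two out of three symptoms are present a UTI is confirmed". A home urine test is requested only when a single symptom is present. SAP 4.12 keeps this, making "A total number of symptoms ≥ 2" sufficient alone. SAP 4.12 treats a confirmed UTI as a separate episode when there was no confirmed UTI in the 14 days before it. Neither document requires a symptom to be new, worse than the woman's usual state, or gone since the last event.

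**Entry.** Exclusion 8 (Protocol 10.5) reads "History of complicated cystitis, urgency incontinence, recent pyelonephritis, urological and/or gynaecologist abnormalities, as judged by the Investigator". Exclusion 10 adds any clinically significant disorder that in the investigator's opinion may "influence the results or the subject's ability to participate in the study". Inclusion 4 (Protocol 10.4) opens with "Recurrent UTI, otherwise healthy".

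**How entry is checked.** Protocol 12.3.4: "Medical/surgical history will be obtained during the screening interview to confirm eligibility". Protocol 12.3.5: "Information regarding previous UTIs (diagnosis, prescriptions, etc.) during the last 12 months will be collected to confirm eligibility". The interview is by phone or video, inclusion 5 requires current antibiotic treatment for a UTI, and Protocol 7.4.1 states: "No clinical assessments will be performed in this study".

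**Analysis.** The primary analysis is an analysis of covariance on the UTI count. SAP 4.7 gives outliers no separate handling. SAP 7.1.2 and 7.1.3 plan no sensitivity or supplementary analysis of the primary endpoint.

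**The concern.** Frequency and urgency can persist for reasons other than infection. With an endpoint that accepts these two symptoms without a test or a comparison with baseline, either the entry criteria or the event definition has to keep such states out of the count. Exclusion 8 names the form with leakage; the form without leakage is not named anywhere. Because screening takes place during treatment of a UTI, symptoms at that moment do not show what is usual for the woman, and no usual level is recorded for later comparison.

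The protocol accepts the principle elsewhere: section 10.6.1 restricts new unprotected partners because chlamydia can resemble a UTI.

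Counts from a stable non-infectious state cannot be prevented by the product. They add the same events to both arms on average, widen the spread of a count with planned means of 0.75 and 1.35, and so lower the chance of detecting a true effect.

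**Working it through.** **1. The plan's own sample size.** Inputs from Protocol 16.2: means 0.75 and 1.35 (difference 0.60), SD 1.15, 5% significance, 80% power, 1:1 allocation. Protocol 16.1 makes the tests two-sided. A two-sample t-test needs 58.6, so 59 per arm, 118 in total, which matches the plan. Power at 59 per arm is 80.2%. For dropout, 118/0.85 = 138.8, so 139, or 140 for equal arms.

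**2. Does the 14-day rule merge the calls?** Calls are planned at Days 30, 60, 90, 120, 150 and 180, each ±7 (Protocol Table 9.1). The shortest planned gap is (60 − 7) − (30 + 7) = 53 − 37 = 16 days. This exceeds 14, so events recorded only at calls stay separate. Six calls allow at most six counts.

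**3. Shift from one woman.** With 70 per arm, a woman scoring 6 in place of an average woman moves her arm's mean by:
- placebo: (6 − 1.35)/70 = 0.066, and 0.066/0.60 = 11%
- probiotic: (6 − 0.75)/70 = 0.075, and 0.075/0.60 = 12.5%

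**4. Effect on power.** Assumption, not in the documents: a share f of each arm scores K whatever the product, and the rest follow the planned distribution.

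- Difference = 0.60 × (1 − f)
- Variance in an arm with mean m = (1 − f) × 1.15² + f(1 − f)(K − m)², averaged over the two arms

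Example, f = 2%, K = 6:
- Difference = 0.60 × 0.98 = 0.588
- Probiotic variance = 0.98 × 1.3225 + 0.0196 × 5.25² = 1.296 + 0.540 = 1.836
- Placebo variance = 1.296 + 0.0196 × 4.65² = 1.296 + 0.424 = 1.720
- Average 1.778, so SD = 1.333, and t-test power at 59 per arm is 66.1%

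| f | Difference | SD, K=6 | Power, K=6 | Power, K=3 | Power, K=1 |
|---|---|---|---|---|---|
| 0 | 0.600 | 1.150 | 80.2% | 80.2% | 80.2% |
| 1% | 0.594 | 1.246 | 72.8% | 78.7% | 79.8% |
| 2% | 0.588 | 1.333 | 66.1% | 77.1% | 79.4% |
| 5% | 0.570 | 1.557 | 50.5% | 72.5% | 78.1% |

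At K = 6, restoring 80% power would take 142, 164 and 238 evaluable women for f = 1%, 2% and 5%, against 118 planned. Two percent of 140 is 2.8, about three women. Like the plan's own calculation, these figures take no credit for covariate adjustment.

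**The case against.** **Entry is not an open door.** A reader might infer that exclusion 8 stops only urgency incontinence and that a woman with standing symptoms passes every criterion. The text does not support that. Exclusion 8 also lists urological abnormalities, exclusion 10 reaches anything that may affect the results, and inclusion 4 requires good health apart from UTI. An investigator who learns of the symptoms can refuse her. She must also be on antibiotics for a UTI and have a recurrent history, which narrows the group. These points stand. What remains is that the decision rests on unguided judgement by interview, and that no stated criterion requires the symptom to be asked about.

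**The question wording is not in the documents.** The pre-screening and monthly questions are described as pre-defined but not reproduced, and may already ask about usual or new symptoms. Only the absence of such a rule from the protocol and SAP can be asserted. Even so, the SAP derivation as written would still count unchanged symptoms.

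**Six counts is an upper bound.** Diary-reported events enter SAP 4.12, and one falling within 14 days before a call makes the call event non-unique. Continuous logging could reduce the run to a single episode. The SAP does not say whether the look-back uses all confirmed events or only unique ones, and it also re-dates site-registered events.

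**A seventh count on Day 1** might be inferred from Table 9.1. Its column alignment is not reliable enough for that. The narrative sections put the symptom questions at the monthly assessments and describe the early contact only as a first-dose check.

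**No systematic bias.** Randomisation and blinding balance such women across arms on average. Chance imbalance between arms is the same added variance, not a second harm.

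**Conclusion.** The concern holds in a limited form. Applied as written, the two-symptom rule counts a stable non-infectious state, and the 14-day rule does not prevent repeat counts at monthly calls. The entry criteria permit refusal of such women but do not name the condition.

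The size depends on two quantities that the documents do not give: the share of such women and how many counts each collects. Over an assumed 1% to 5%, the loss of power runs from negligible (one count each) to about 30 points (six counts each at 5%). The lower figures should not be quoted without the assumptions behind them. One woman at the maximum moves her arm's mean by 0.07 to 0.08, or 11% to 13% of the planned difference. A reader might take 6/70 = 0.09 (14%), but that compares her with a woman who has no UTI, not with the average woman in her arm.

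This warrants a change because a stated counting rule gives wrong counts and the planned primary analyses contain nothing that would reveal it.

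**What to change.** 1. In the monthly questions and in SAP 4.12, count a symptom towards the two-symptom rule only if it is new or worse than the woman's usual state between infections. This is the main change, since it works even when screening misses someone.
2. Add to exclusion 8 usual urinary frequency or urgency between infections, with or without incontinence, asked as one fixed question in the existing screening call.

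The cost is an amendment, one screening question and a wording change; no visit or test is added. A few otherwise eligible women would be refused, and the usual state is self-reported. The change has to be in place when the questions are asked, because SAP wording alone cannot recover whether a recorded symptom was new.
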